11.1. Definitions/Classifications

11.1.1. Adverse Event (AE)

In alignment with ISO 14155:2011 (Section 3.2), an Adverse Event is any untoward medical occurrence, unintended disease or injury, or untoward clinical signs (including abnormal laboratory findings) in subjects, users or other persons, whether or not related to the investigational medical device.

This definition includes events related to the study device and the procedures involved. For users or other persons, this definition is restricted to events related to study devices.

For study purposes, the following occurrences are considered to be expected observations following surgical procedures (primarily associated with anesthesia) and will not be considered reportable AEs, as long as the event is not associated with significant sequelae, does not prolong hospitalization, and responds to standard medical therapy:

- Postoperative transient nausea determined to be procedure related within the first 24 postoperative hours.
- Postoperative transient emesis determined to be procedure related within the first 24 postoperative hours.
- Postoperative constipation, determined to be procedure and/or medication related for the duration of medication administration for management of pain.
- Postop pain that the Investigator considers common and within normal limits for the procedure and is well-managed with medication.

For study purposes procedure related adverse events will be collected and documented at the time of the procedure and up to and including the 30 day (+14 days) post-operative follow up visit.

11.1.2. Serious Adverse Events (SAE)

In alignment with ISO 14155:2011 (Section 3.37), a serious adverse event (SAE) is any AE that has:

- led to death,
- led to serious deterioration in the health of the subject that either resulted in
 - o a life-threatening illness or injury, or
 - o a permanent impairment of a body structure or a body function, or
 - in-patient or prolonged hospitalization, or
 - medical or surgical intervention to prevent life threatening illness or injury or permanent impairment to a body structure or a body function, or
- led to fetal distress, fetal death, or a congenital abnormality or birth defect.

MDT17025SIG Version 3.0 Page 39 of 57

NOTE: Planned hospitalization for a pre-existing condition or a procedure required by the clinical investigational plan, without serious deterioration in health, is not considered an SAE.

SAEs will be collected and documented at procedure and up to and including the 30 day (+14 day) post-operative follow-up visit.

11.1.3. Adverse Device Effect (ADE)

In alignment with ISO 14155:2011 (Section 3.1), an Adverse Device Effect is an adverse event related to the use of an investigational medical device.

This definition includes adverse events resulting from insufficient or inadequate instructions for use, deployment, implantation, installation, or operation, or any deficiency/malfunction of the investigational medical device.

This definition includes any event resulting from use error or from intentional misuse of the investigational medical device.

Adverse Device Effects will be reported by the Investigator(s). If escalation is required (due to the potential need for reporting) ADEs will be reviewed by Medtronic Medical Affairs. Both confirmed and possible adverse device effect events will be included in the study report.

Examples of adverse device effects include but are not limited to: leaking or bleeding due to non-functional staple closure, damage to surrounding tissue due to unintentional firing, unintentional tissue loss due to reload locks on tissue

ADEs will be collected and documented at procedure and up to and including the 30-day follow-up visit.

11.1.4. Serious Adverse Device Effect (SADE)

In alignment with ISO 14155:2011 (Section 3.36), a Serious Adverse Device Effect is an adverse device effect that has resulted in any of the consequences characteristic of a serious adverse event.

SADEs will be collected and documented at procedure and up to and including the 30-day follow-up visit.

11.1.5. Unanticipated Serious Adverse Device Effect (USADE)

In alignment with ISO 14155:2011 (Section 3.42), an Unanticipated Serious Adverse Device Effect is a serious adverse device effect which by its nature, incidence, severity, or outcome has not been identified in the current version of the risk analysis report.

NOTE: Anticipated serious adverse device effect (ASADE) is an effect which by its nature, incidence, severity or outcome has been identified in the risk analysis report.

MDT17025SIG Version 3.0 Page 40 of 57

USADEs will be collected and documented at procedure and up to and including the 30-day follow-up visit.

11.1.6. Device Deficiencies

In alignment with ISO14155:2011 (Section 3.15), a Device deficiency is an inadequacy of a medical device-related to its identity, quality, durability, reliability, safety or performance; such as malfunction, misuse or use error and inadequate labeling.

All Signia™ Stapling System device deficiencies/malfunctions will be documented on the Device Deficiency/Malfunction eCRF.

In the event of a device deficiency the device should be returned to Covidien for analysis, if possible. Instructions for returning the study device will be provided. Device deficiencies should also be documented in the subject's medical record.

Device deficiencies are NOT to be reported as AEs.

However, if there is an AE that results from a device deficiency, that specific event would be recorded on the appropriate eCRF.

11.1.7. Adverse Event Severity Classification

Severity will be defined according to the following criteria:

Mild	Awareness of event, but easily tolerated
Moderate	Discomfort enough to cause some interference with activities of daily living (ADL)
Severe	Incapacitating, with an inability to perform ADL
Death	Death related to AE

An AE can be classified as severe and not deemed an SAE. Similarly, an SAE is not automatically severe in nature.

11.1.8. Adverse Event Relationship Classification

Causality assessments define the relationship between the use of the medical device (including the medical-surgical procedure) and the occurrence of each adverse event, according to MEDDEV (Guidelines on Medical Devices, Clinical Investigations: Serious Adverse Event Reporting). The presence of confounding factors, such as concomitant medication/treatment, the natural history of the underlying disease, other concurrent illness or risk factors shall also be considered.

Each AE will be classified according to five different levels of causality. The sponsor and the investigators will use the following definitions to assess the relationship of the serious adverse event to the investigational medical device or procedures:

MDT17025SIG Version 3.0 Page 41 of 57

Not related: relationship to the device or procedures can be excluded when:

- 1. the event is not a known side effect of the product category the device belongs to or of similar devices and procedures
- 2. the event has no temporal relationship with the use of the device or the procedures;
- 3. the serious event does not follow a known response pattern to the medical device (if the response pattern is previously known) and is biologically implausible;
- 4. the discontinuation of medical device application or the reduction of the level of activation/exposure when clinically feasible and reintroduction of its use (or increase of the level of activation/exposure), do not impact on the serious event;
- 5. the event involves a body-site or an organ not expected to be affected by the device or procedure;
- 6. the serious event can be attributed to another cause (e.g. an underlying or concurrent illness/clinical condition, an effect of another device, drug, treatment or other risk factors);
- 7. the event does not depend on a false result given by the device used for diagnosis, when applicable;
- 8. harms to the subject are not clearly due to use error;
- 9. In order to establish the non-relatedness, not all the criteria listed above might be met at the same time, depending on the type of device/procedures and the serious event.

Unlikely: the relationship with the use of the device seems not relevant and/or the event can be reasonably explained by another cause, but additional information may be obtained.

Possible: the relationship with the use of the device is weak but cannot be ruled out completely. Alternative causes are also possible (e.g. an underlying or concurrent illness/ clinical condition or/and an effect of another device, drug or treatment). Cases were relatedness cannot be assessed or no information has been obtained should also be classified as possible.

Probable: the relationship with the use of the device seems relevant and/or the event cannot reasonably be explained by another cause, but additional information may be obtained.

Causal relationship: the serious event is associated with the device or with procedures beyond reasonable doubt when:

- 1. the event is a known side effect of the product category the device belongs to or of similar devices and procedures;
- 2. the event has a temporal relationship with device use/application or procedures;
- 3. the event involves a body-site or organ that
 - a. the device or procedures are applied to;
 - b. the device or procedures have an effect on;
- 4. the serious event follows a known response pattern to the medical device (if the response pattern is previously known);

MDT17025SIG Version 3.0 Page 42 of 57

- the discontinuation of medical device application (or reduction of the level of activation/exposure) and reintroduction of its use (or increase of the level of activation/exposure), impact on the serious event (when clinically feasible);
- 6. other possible causes (e.g. an underlying or concurrent illness/ clinical condition or/and an effect of another device, drug or treatment) have been adequately ruled out;
- 7. harm to the subject is due to error in use;
- 8. the event depends on a false result given by the device used for diagnosis, when applicable;
- 9. In order to establish the relatedness, not all the criteria listed above might be met at the same time, depending on the type of device/procedures and the serious event.

The Sponsor and the Investigators will distinguish between the serious adverse events related to the device and those related to the procedures (any procedure specific to the clinical investigation). An adverse event can be related both to procedures and the device. Complications of procedures are considered not related if the said procedures would have been applied to the subjects also in the absence of device use/application.

In some particular cases the event may be not adequately assessed because information is insufficient or contradictory and/or the data cannot be verified or supplemented. The sponsor and the Investigators will make the maximum effort to define and categorize the event and avoid these situations. Where the sponsor remains uncertain about classifying the serious event, it should not exclude the relatedness and classify the event as "possible".

Particular attention shall be given to the causality evaluation of unanticipated serious adverse (device) events. The occurrence of unanticipated events related to the use of the device (USADE) could suggest that the clinical investigation places subjects at increased risk of harm than was to be expected beforehand

11.1.9. Adverse Event Outcome Classification

Outcome of the event will be defined according to the following:

[figure not shown]
- Fatal: This event is determined to be the cause of death.
- Not Recovering/Not Resolved: The event has retained pathological conditions resulting from the
 prior disease or injury.
- **Recovered/Resolved**: The event has fully resolved at the end of the study.
- Recovering/Resolving: The event is ongoing at the end of the study.
- *Unknown*: The event has been unclassified at the end of the study.

11.2. Reporting of Adverse Events

The following events are generally considered reportable during the course of this study and should be reported to the sponsor:

any device related AE, SADE, SAE, or USADE

- any Device Deficiency/Malfunction that might have led to a SADE if
 - o suitable action had not been taken or
 - o intervention had not been made or
 - o if circumstances had been less fortunate
- new findings/updates in relation to already reported events.

Events will be reviewed by the sponsor to determine any reporting obligations to National Competent Authorities and IRBs/ECs.

The following table captures the reporting requirements for this study. Local and regional regulatory requirements shall be followed in addition to study requirements.

Type of Event	Timeframe	Submit to
Any Death	As soonas practicable but no more than 10 work days after the day that you become aware of information from any source, that reasonably suggests that a device has or may have caused or contributed to the death of a patient of your facility	Sponsor/ Device Manufacturer and Local (IRB/EC) and regional regulators (FDA)
UADE	As soonas possible, but in no event later than 10 working days after the investigator first learns of the effect.	Sponsor / Device Manufacturer and any local/ regionally required regulators
All Serious Events including SAEs, USADEs, Serious Injuries or Significant Safety Issues	Within 24 hours, but no later than 10 work days (and/or per local requirements) after the day that investigator becomes aware of information, from any source, that reasonably suggests that a device has or may have caused or contributed to a serious injury to a patient of your facility.	Sponsor / Device Manufacturer and as per local reporting requirements.

MDT17025SIG Version 3.0 Page 45 of 57

Assessment of the occurrence of an AE will be based on changes in the subject's abbreviated physical examination, laboratory results and/or signs and symptoms. Adverse events will be monitored until a subject completes the study unless the Investigator determines the event is related to the device, in which case they will be monitored until resolution if possible. Medical care will be provided, as defined in the informed consent, for any AE related to study participation. Adverse events will be collected on an AE eCRF and applicable source documentation. To the extent possible, the event to be recorded and reported is the event diagnosis as opposed to event symptoms (e.g., fever, chills, nausea and vomiting in the presence of a clinically diagnosed infection is to be reported as infection only). For the purposes of this protocol, only those AEs occurring after enrollment will be recorded.

The following should not be considered an AE:

- A condition requiring a preplanned procedure unless the condition worsened since screening
- A preexisting condition found as a result of screening, unless the condition has worsened since enrollment

All responses to the above events that require treatment beyond the institution's standard procedures will be reported as AEs.

All device and procedure related AEs observed during the course of this study (up to and including the 30day follow up visit), regardless of severity or relationship to the device will be recorded on the appropriate eCRF.

12.1. Safety Committee

An internal Medtronic Safety Team will review the overall rates of protocol defined adverse events (SAEs and events related to the primary and secondary endpoints) on a quarterly basis. The committee will have the ability to make recommendations and request further information as required.

12.2. Independent Medical Monitor

Medtronic will utilize an Independent Medical Monitor to provide an independent adjudication of prespecified adverse events in support of protocol defined endpoint data. The Independent Medical Monitor will be a qualified, board-certified surgeon that is not affiliated with an investigative center. The Independent Medical Monitor will contribute to safety aspects of the clinical study and will conduct the study Safety Review Meetings and will review the key events and data in the event of Serious Adverse Events.

The Independent Medical Monitor will be blinded to the investigational sites.

12.3. Steering Committee

The Steering Committee will consist of Investigators participating in this study, as well as appropriate members of Medtronic Clinical and Medical Affairs. The role of the Steering Committee is to make recommendations on the design and conduct of the study, the analysis of data, and the communication of results in alignment with the Medtronic Publication and Authorship Policy. The Steering Committee will also review aggregate adverse event data on an as needed basis, as described in the Steering Committee Charter.

13. Statistical Design and Methods

13.1. Statistical Test Methods

Continuous variables will be summarized using counts, means, standard deviations, medians, minimum and maximum. Categorical variables will be summarized using frequencies and percentages. Changes to the planned statistical analysis as defined in the protocol will be documented in the statistical analysis plan and clinical study report.

13.2. Sample Size Determination

Sample size was determined based on the primary endpoint (incidence of subjects reporting serious adverse device effects (ADEs) up to and including 30 days including intra- and post-operative leaks), but considering an acceptable probability (≥ 80%) to observe at least one adverse device effect (ADE) within 30 days, in each arm (abdominal or thoracic indication).

A previous Medtronic study (ClinicalTrials.gov ID NCT02500537) conducted on N=100 subjects and evaluating an equivalent device (Endo GIA™ Reinforced Reload with Tri-Staple™ Technology) in the same indications and with a similar design and follow-up reported the following adverse device effects rates (described as "device related adverse events" with the study protocol and final report):

	Abdominal	Thoracic
Adverse device effect incidence	3.3%	2.5%

Because of the expected low adverse device effect incidence rate (<5%) in the Abdominal or Thoracic procedures, as described above, a Poisson distribution is applied to estimate the probability of observing AE event(s).

In the Abdominal indication, for an anticipated sample size of 53 subjects using an adverse device effect rate of 3.3%, and including a 5% attrition rate within 30 days, we obtain a probability of 81% to observe at least 1 adverse device effect.

In the Thoracic indication, for an anticipated sample size of 74 subjects using an adverse device effect rate of 2.5%, and including a 5% attrition rate within 30 days, we obtain a probability of 83% to observe at least 1 adverse device effect.

For the overall population (in both indications), with a sample size of 127 subjects and considering an averaged adverse device effect rate of 2.9%, and including a 5% attrition rate within 30 days, we obtain a probability of 97% to observe at least 1 adverse device effect, and a probability of 86% to observe at least 2 adverse device effects.

In any scenario, we will have $\geq 80\%$ probability to observe at least 1 adverse device effect in each arm.

13.3. Analysis Population

The full analysis set (FAS) will consist of all enrolled and treated subjects (using Signia[™]). For this study the full analysis set corresponds to the safety population. FAS will serve as the primary analysis population for safety and performance analyses, as well as for demographics and baseline data analysis.

MDT17025SIG Version 3.0 Page 48 of 57

The per protocol (PP) population will consist of all subjects from the FAS population who do not have a major protocol violation. Analyses on the PP population will provide supporting evidence to the primary results (obtained on FAS).

13.4. Statistical Analysis Endpoints

13.4.1. Primary Endpoint

The primary endpoint is the incidence of subjects reporting serious adverse device effects up to and including 30 days (+14days) post-procedure which utilizes the Signia™ Stapling System. It will be summarized using descriptive statistics.

A two-sided 95% confidence interval will also be calculated. The acceptance criteria for this endpoint is an upper limit of the 95% CI below 20%.

The analysis will be performed in abdominal group and in thoracic group, and in the combined groups.

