7.1.3. Analysis Sets

SIGNIA Statistical Analysis Plan	
Version [Final#1.0] Page 12 of 15	Medtronic

Full Analysis Set (FAS): includes all enrolled and treated subjects (using Signia[™]). For this study, the Full analysis set corresponds to the safety population. FAS will serve as the primary analysis population for safety and performance analyses, as well as for demographics and baseline data analysis.

The per protocol Analysis Set (PPAS): includes all subjects from the FAS population who do not have a major protocol violation. Analyses on the PPAS will provide supporting evidence to the primary results (obtained on FAS).

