7.2. General Methodology

Statistical analysis will be descriptive, and run separately in each arm:

- Continuous variables will be summarized using counts, means, standard deviations, medians, minimum and maximum.
- Categorical variables will be summarized using frequencies and percentages. Changes to the planned statistical analysis as defined in the protocol will be documented in the statistical analysis plan and clinical study report.

Some subgroup comparative analyses may be run in addition to primary and secondary endpoints, to assess impact of demographic characteristics, risk-factors, and surgery technique on the performance and safety outcomes.

In case of comparative analysis is performed:

- Pearson Chi-square test or Exact test will be used (as appropriate) for categorical data
- Student t-test or Wilcoxon rank sum test will be used if assumptions of t-test are not verified for continuous data.

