7.3. Center Pooling

The study will be conducted in a minimum of 4 investigational sites. Screening and surgical data will be summarized for overall subjects and for each site separately, to confirm homogeneity of subject's characteristics between sites.

Primary and secondary endpoint analysis will be run on overall subjects. In case of imbalance regarding subject's characteristics between sites, additionnal subgroup analyses for primary and secondary endpoints could be performed according to investigational sites.

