7.9. Evaluation of Objectives

Study objectives will be assessed through study endpoints measurement.

The primary endpoint is the incidence of subjects reporting serious adverse device effects up to and including 30 days (+14days) post-procedure which utilizes the Signia[™] Stapling System. It will be summarized using descriptive statistics.

A two-sided 95% confidence interval will also be calculated.

The analysis will be performed in abdominal group and in thoracic group, and in the combined groups, based on Full analysis Set, as defined previously. A confirmatory analysis of primary endpoint will be run using Per Protocol Analysis Set.

Secondary endpoints

SIGNIA Statistical Analysis Plan Medtronic Version [Final#1.0] Page 14 of 15

The secondary endpoint is device deficiency/malfunction affecting the intended performance of the device to include;

- Staple line assessment:
 - Intraoperative assessments:
 - Assessment of staple line integrity
 - Incidence of staple line bleeding (measured as \geq 50 cc)
 - Additional intervention(s) to treat staple-line failure (ex: glue, manual over sew, Medtronic buttress) or intraoperative revision/recreation of the anastomosis
 - Incidence of leakage (as measured by air leak test, or standard of care, as applicable)
 - Post-operative assessments:
 - Duration of air leakage (in days) for thoracic procedures
 - Prolonged air leaks are considered >7 days
 - Incidence of leakage for abdominal procedures as evidenced confirmed by imaging subject presentation or decline in status, or need for reoperation/re-intervention
 - Incidence of post-operative infection, assessed by the Investigator according to the standard of care and site policy, ex. positive wound culture
 - Additional intervention(s) to treat staple-line failure
- Incidence of repeat hospital admissions for primary procedure-related complications.

Secondary endpoints analysis will be run on Full Analysis Set and on Per-Protocol Analysis Set.

All recorded device deficiencies/malfunctions will be captured and assessed by the Investigator. Complaints will be handled in accordance with the standard procedures for the post-market vigilance system.

7.10.Safety Evaluation

Safety will be assessed as the proportion of subjects with AE based on the FAS, and on PPAS. AE incidence will be reported overall, and according to:

- Relation to the procedure
- Relation to the device including anticipated and unanticipated ADEs, related to:

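### Does the SAP's silence on the protocol's 20% acceptance limit, and its wording on arms and overall subjects, leave the primary endpoint without a verdict?

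*Protocol*

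**What the plan says.** Protocol 13.4.1, like the synopsis, summarises the primary endpoint descriptively with a two-sided 95% interval and adds: "The acceptance criteria for this endpoint is an upper limit of the 95% CI below 20" percent. The next sentence reads "The analysis will be performed in abdominal group and in thoracic group, and in the combined groups". It does not say which of the three must meet the limit.

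SAP 7.9 keeps the endpoint and the interval ("A two-sided 95% confidence interval will also be calculated"), names the same three groups and places the analysis on the full analysis set (FAS). The 20% limit appears nowhere in the SAP, and no change from the protocol is recorded, although Protocol 13.1 says that changes will be documented there.

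Three other SAP statements bear on the point:
- 7.2, General Methodology: "Statistical analysis will be descriptive, and run separately in each arm".
- 7.3, Center Pooling: "Primary and secondary endpoint analysis will be run on overall subjects".
- 7.9, on the per-protocol set: "A confirmatory analysis of primary endpoint will be run using Per Protocol Analysis Set". SAP 7.1.3 and Protocol 13.3 give that set a supporting role only.

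Neither document names the interval method. Protocol 13.6 and SAP 7.8 plan a preliminary analysis at 64 subjects and attach no acceptance limit to it.

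**The concern.** The limit is the protocol's only pass/fail rule, and the document the programmers work from lacks it. Read alone, SAP 7.2 points to each arm and SAP 7.3 to everyone together. The combined group is the easier test because it has more subjects, so a choice made after the counts are known could only favour the device. The unnamed interval method and the word used for the per-protocol analysis look like further freedom. The interim seems most exposed: its arms are small, and its result is meant to support a regulatory submission.

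**Working it through.** **The plan's own figures.** Protocol 13.2 gives 53 abdominal and 74 thoracic subjects, any-device-effect rates of 3.3% and 2.5% (2.9% overall) and 5% attrition. With L = 0.95 × n × p and P(at least 1) = 1 − exp(−L):
- abdominal: L = 0.95 × 53 × 0.033 = 1.662, giving 81.0% (stated 81%);
- thoracic: L = 0.95 × 74 × 0.025 = 1.758, giving 82.8% (stated 83%);
- overall: L = 0.95 × 127 × 0.029 = 3.499, giving 97.0% (stated 97%). P(at least 2) = 1 − exp(−L)(1 + L) = 86.4% (stated 86%).

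All reproduce. None uses the 20% limit.

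**What the limit allows.** The Clopper-Pearson upper limit for x of n is the 0.975 quantile of Beta(x + 1, n − x).

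| Group | Largest passing count | Upper limit | Next count | Upper limit |
|---|---|---|---|---|
| Abdominal | 4/53 | 18.2% | 5/53 | 20.7% |
| Thoracic | 7/74 | 18.5% | 8/74 | 20.2% |
| Combined | 16/127 | 19.7% | 17/127 | 20.6% |

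If both arms pass, the total is at most 4 + 7 = 11, so the combined group passes too. The reverse can fail: 5/53 and 8/74 both miss, while 13/127 passes (16.9%).

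**How often the verdicts differ at the final analysis.** Take X and Y as independent binomial counts. P(both arms pass) = P(X ≤ 4) × P(Y ≤ 7), and P(combined passes) = P(X + Y ≤ 16). The difference is the probability that the combined group passes and an arm misses.

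| Rates, abdominal/thoracic | Both arms pass | Combined passes | Difference |
|---|---|---|---|
| 1.65%/1.25% (assumption: half) | 0.998 | 1.000 | 0.002 |
| 3.3%/2.5% (planning, any effect) | 0.9697 × 0.9995 = 0.969 | 1.000 | 0.031 |
| 5%/5% (assumption) | 0.8754 × 0.9686 = 0.848 | 0.9998 | 0.152 |
| 10%/10% (assumption) | 0.3782 × 0.5363 = 0.203 | 0.868 | 0.665 |

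The expected counts at the planning rates are 53 × 0.033 = 1.7 and 74 × 0.025 = 1.9, against 4 and 7 allowed. These rates cover every device effect, whereas the endpoint counts serious ones.

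**Interval method.** Wilson gives 4, 8 and 16, one event different in one group. The Wald interval gives 6, 9 and 17.

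**Interim.** Splitting 64 in the planned proportion (64 × 53/127 ≈ 27, leaving 37; an assumption) gives boundaries of 1/27, 2/37 and 6/64. At the planning rates the difference is 0.998 − 0.726 = 0.272; at half, 0.083. Both need the limit to be read at the interim, which neither document says. They also depend on whole-number cut-offs: at the planning rates a 25/39 split gives 60% and a 26/38 split 26%.

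**The wording side by side.** SAP 7.2 is a general rule. SAP 7.9 is specific to the primary endpoint and lists the same three groups as Protocol 13.4.1. In SAP 7.3 the sentence before the quoted one contrasts all subjects with each site taken separately, and the sentence after it falls back on subgroups by site. There, overall means pooled over sites. The three sections are compatible.

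**The case for a change.** The strongest case for a change is that SAP 7.9 drops one sentence from a paragraph it otherwise repeats, records no change, and that sentence is the acceptance rule. Restoring it and naming the governing group, the analysis set, the interval method and the interim's status would need only wording. The unstated choice can err only toward a favourable claim, and at serious rates of 5% or 10% the verdicts would differ 15% or 67% of the time.

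The omission stands as a fact, and so does the lack of a stated governing group. The rest carries less weight. SAP section 3 says the SAP was built from the protocol, and silence there does not withdraw a limit that the protocol states twice. The natural reading of 13.4.1 applies the limit in each listed group. The other reading, combined only, is a choice open to the sponsor: at the planning rates it passes with probability 100% against 97%. Either way all three intervals are reported, so a reader can hold each against 20%.

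The analysis-set example (5/53 misses at 20.7%, while 4/52 after one exclusion passes at 18.5%) shows only a sensitivity result that differs, because both documents make the FAS primary. Nor is an edit to the protocol free: Protocol 15.6 sends amendments through sponsor, IRB/EC and any regulatory approval, with site training.

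**Conclusion.** No change is needed. The SAP leaves out a limit that remains in force in the protocol, and an analyst holding both documents would apply it to the three FAS intervals. Naming an interval method is detail that analysts fill sensibly, and an exact method is the usual choice for low counts. Which group governs is a fair trade-off, and its consequence at the final analysis is small: 3% at the planning rates, 0.2% at half. The apparent clash between SAP 7.2 and 7.3 disappears on reading 7.3 in context, and the label on the per-protocol analysis in 7.9 is a slip of wording.

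This rests on Clopper-Pearson intervals, independent arms at the planned sizes, and serious device-effect rates no higher than the any-effect planning rates. It also takes leaks to count only when they are serious and device-related. At clearly higher rates the arm and combined verdicts would often differ, but the reported intervals would show it. The interim figures matter only if the limit is read there, and the plan does not provide for that.
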